2.3.2. Benefit Assessment

Etrasimod is not expected to provide any clinical benefit to healthy participants. This sub study is designed primarily to assess the feasibility of conducting a Phase 1 etrasimod study as a hybrid decentralized clinical trial with dosing by study personnel at the CRU and remote collection of PK, safety and tolerability data. In this study, etrasimod will be administered at single doses of 2 mg.

2.3.3. Overall Benefit/Risk Conclusion

Taking into account the measures to minimize risk to study participants, the potential risks identified in association with etrasimod are justified by the anticipated benefits that may be afforded to participants with UC.

3. OBJECTIVES AND ENDPOINTS

Objectives	Endpoints
Primary:	Primary:
To compare the PK of etrasimod 2 mg clinical IR tablets under fasted conditions in healthy participants using Tasso PK micro samples taken by participants only (Treatment G) vs. CRU staff and participants (Treatment F) in a hybrid DCT design	Plasma AUC _{24 hr} , AUC _{24hr-last} , AUC _{inf} (if data permit, otherwise AUC _{last}) and C _{max} of etrasimod
Secondary:	Secondary:
To compare the PK of etrasimod 2 mg clinical IR tablets under fasted conditions in healthy participants using Tasso PK micro samples taken by participants only (Treatment G) vs. CRU staff and participants (Treatment F) in a hybrid DCT design vs. venous PK samples taken by CRU staff in conventional design of main study (Treatment A)	Plasma AUC _{24 hr} , AUC _{24hr-last} , AUC _{inf} (if data permit, otherwise AUC _{last}) and C _{max} of etrasimod
To evaluate the safety and tolerability of etrasimod mg clinical IR tablets in healthy participants using mobile wearable devices in a hybrid DCT design	Assessment of first dose HR reduction, TEAEs, clinical laboratory abnormalities, vital signs, PEs, and ECGs
Tertiary/Exploratory:	Tertiary/Exploratory:
To compare the concentrations of etrasimod in PK samples collected using micro sampling device against those using venous blood sampling.	Plasma concentrations of etrasimod obtained via micro sampling compared to venous sampling at pre-dose and at 2 and 4 hrs post-dose.

4. STUDY DESIGN

4.1. Overall Design

This is a Phase 1, open-label, single-dose, fixed-sequence, crossover sub study in a single cohort of approximately 8 healthy male or female participants conducted using a hybrid DCT design.

The study will consist of 2 treatments. Participants will receive the two Treatments F and G in a fixed sequence as shown below.

Fixed Treatment Sequence (n=8)	Period 1	Period 2
	F	G

Treatment F: Single oral dose of etrasimod 2 mg, DCT with practice sessions* (Reference)

Following are the key elements of the design of this hybrid decentralized clinical trial. Participants will be discharged from the CRU on Day 2 of each Period, following practice sessions (Period 1 only) with the use of Tasso for serum PK sampling and wearable devices for safety monitoring, and the completion of all assessments that are planned to be performed at the CRU. The Tasso OnePlus, high-volume liquid blood collection device, will be used for micro-PK sampling and the blood samples collected by participants will be sent to the CRU within 72 hours of collection for processing of serum. The BioBeat Patch and PCA500 wearable monitoring devices will be used for collection of vitals and ECGs, respectively, in Periods 1 and 2. Each treatment period is 8 days that includes dosing, PK sampling, safety assessments, and practice (Period 1 only) with use of wearable devices and Tasso sampling. The PK and safety (ECGs and vitals) assessments through Day 2 of Period 1 will be performed by the CRU staff. Following practice with the Tasso and wearable monitoring devices on Day 2 of Period 1, the assessments on Days 3 to 8 (remote) of Period 1 and on Days -1 to 2 (at CRU) and 3 to 8 (remote) of Period 2 will be self-performed by the participants. Participants will be discharged from the CRU on Day 2 Periods 1 and 2. Participants will receive an emergency card for contacting the CRU and will be provided detailed instructions to call PCRU for reporting of an AE. Additionally, the participants will be provided with diaries to record information about PK sampling times, concomitant medication(s) and AEs during the self-assessment phase following discharge on Day 2 of Periods 1 and 2. The participants will be provided instructions for returning the wearable devices and other study related materials study following completion of all assessments on Day 8 of Period 2. The total planned duration of participation from the screening visit to the last follow-up phone call, is approximately 9 weeks.

Since etrasimod has a half-life approximately 30 hours, there will be an 8-day washout between each dose.

In both Periods 1 and 2, capillary blood samples (using micro sampling Tasso device) for PK analysis will be collected at predose and at 1, 2, 4, 6, 8, 12, 24, 48, 72, 96, 120, 144 and 168 hours postdose (SoA). Venous blood samples for PK analysis will be collected predose and at 2 and 4 hours postdose (SoA). Micro PK sampling occurs after venous PK blood sampling; samples will be taken from the alternate arms from one sampling time to the next.

Participants will be screened within 28 days of the first dose of study intervention and if all entry criteria are fulfilled, the participants will report to the CRU on the day prior to Day 1 dosing (Day -1). On Day 1 of each period, participants will receive a single dose of study intervention at the CRU. Administration of etrasimod will be oral via dosing of clinical IR

Treatment G: Single oral dose of etrasimod 2 mg, DCT without practice sessions** (Test)

^{*} Practice of Tasso and Wearable Monitoring Devices on Day 2 at CRU; participant self-assessment remotely for vitals and ECG (Days 3-5) and PK samples (Days 3-8)

^{**} Participant self-assessment using Tasso and Wearable Monitoring Devices on Days 1-2 at CRU; and remotely on Days 3-8

tablet 2 mg with water as per dosing instructions. Participants will be fasted for at least 10 hours predosing and 4 hours postdosing.

Participants will be confined in the CRU for a total of at least 2 days and discharged on Day 2 of each Period. A follow-up phone call will be made at least 28 calendar days and up to 35 calendar days after the last administration of the study intervention to capture any potential AEs and confirm appropriate contraceptive usage.

Tolerability and safety will be assessed for all treatments by monitoring AEs. Participants who withdraw from the study or whose PK samples are determined to be non-analyzable may be replaced at the discretion of the of the investigator upon consultation with the sponsor.

4.2. Scientific Rationale for Study Design

The purpose of the sub study is to determine the PK and to assess the safety and tolerability of etrasimod clinical IR tablets 2 mg under fasted conditions in healthy adult participants in a hybrid DCT design. Since etrasimod has a long half-life of approximately 30 hours, requiring blood sampling up to 168 hours post-dose for PK characterization of its PK profile, standard crossover BA study designs can require relatively long CRU stay requirements and may impede participant recruitment and retention. Therefore, this hybrid DCT design sub study is designed to investigate the utility of self-assessment of PK, vitals and ECGs remotely by study participants in two fixed-sequence crossover study Periods, wherein Period 1 will include assessments by CRU staff up to Day 2 and a training session for participants. The participants will perform self-assessments on Days 3 to 8 (remote) of Period 1 and on Days - 1 to 2 (at CRU) and 3 to 8 (remote) of Period 2. On Day 1 of each period, participants will receive a single dose of etrasimod IR tablet 2 mg at the CRU.

4.2.1. Rationale for ECG Measurements

In the heart, $S1P_1$ is expressed on atrial myocytes and is associated with the regulation of heart rate. $S1P_1$ agonism activates both G alpha i (Gi) and β -arrestin signaling pathways. β -arrestin activation leads to receptor internalization, while Gi coupled signaling activates GIRK channels that regulate potassium efflux and membrane potential. As a result, there is a transient, first dose associated, chronotropic (slowing of HR) and dromotropic (slowing of AV nodal conduction) effects associated with etrasimod (a class effect). For all Phase 1 studies, intensive ECG have been taken for the first 6-hours post first dose. For this study, this practice should be in place until the NDA is approved.

4.2.2. Rationale for PR and BP Monitoring

In addition to the transient, first dose associated, chronotropic effect associated with etrasimod, hypertension has been observed with S1P receptor modulators and AEs of hypertension have been reported. For all phase 1 studies, intensive BP and PR monitoring post dose has been undertaken and this will continue for this study.

4.2.3. Choice of Contraception/Barrier Requirements

Etrasimod is known to cause risk for severe manifestations of developmental toxicity in humans or suspected on the basis of the intended pharmacology. Therefore, the use of a

highly effective method of contraception is required for both female and male participants (see Appendix 4).

4.3. Justification for Dose

The dose of etrasimod 2 mg once daily has been shown to be efficacious and safe in moderate to severely active adult UC patients.

This study is designed to evaluate PK of etrasimod 2 mg clinical IR tablet formulation in healthy adult participants.

4.4. End of Study Definition

The end of the study is defined as the date of the last visit of the last participant in the study or last scheduled procedure shown in the SoA and the investigator has reviewed the final safety data and determined that no additional evaluation is required.

A participant is considered to have completed the study if they have completed all periods of the study, including the last visit or the last scheduled procedure shown in the SoA.

5. STUDY POPULATION

This study can fulfill its objectives only if appropriate participants are enrolled, including participants across diverse and representative racial and ethnic backgrounds. If a prescreening tool is utilized for study recruitment purposes, it will include collection of information that reflects the enrollment of a diverse participant population including, where permitted under local regulations, age, sex, race, and ethnicity. The following eligibility criteria are designed to select participants for whom participation in the study is considered appropriate. All relevant medical and nonmedical conditions should be taken into consideration when deciding whether a particular participant is suitable for this protocol.

Prospective approval of protocol deviations to recruitment and enrollment criteria, also known as protocol waivers or exemptions, is not permitted.

5.1. Inclusion Criteria

Participants are eligible to be included in the study only if all of the following criteria apply:

Age and Sex:

- 1. Male and female participants aged 18 years or older (or the minimum age of consent in accordance with local regulations) at screening who are overtly healthy as determined by medical evaluation including a detailed medical history, full physical exam, which includes BP and pulse rate measurement, clinical laboratory tests, temperature, and 12-lead ECG.
 - Refer to Appendix 4 for reproductive criteria for male (Section 10.4.1) and female (Section 10.4.2) participants.

Other Inclusion Criteria:

- 2. BMI of 16 to 32 kg/m²; and a total body weight > 50 kg (110 lb).
- 3. Participants who are willing and able to comply with all scheduled visits, treatment plan, laboratory tests, lifestyle considerations, and other study procedures.
- 4. Capable of giving signed informed consent as described in Appendix 1, which includes compliance with the requirements and restrictions listed in the ICD and in this protocol.
- 5. Capable of using wearable monitoring devices for the duration of this study, according to the requirements specified in the SoA.

5.2. Exclusion Criteria

Participants are excluded from the study if any of the following criteria apply:

Medical Conditions:

- 1. Evidence or history of clinically significant hematological, renal, endocrine, pulmonary, gastrointestinal, cardiovascular, hepatic, psychiatric, neurological, anaphylactic, ophthalmologic disorders (such as macular edema, uveitis, retinopathy), or allergic disease (including drug allergies, but excluding untreated, asymptomatic, seasonal allergies at the time of dosing).
 - Myocardial infarction, unstable angina, stroke/transient ischemic attack, decompensated heart failure requiring hospitalization, or Class III/IV heart failure ≤6 months prior to study intervention
 - Second- or third-degree AV block, sick sinus syndrome without a functional pacemaker, or periods of asystole for >3 seconds without an implanted cardiac defibrillator
 - Recurrent symptomatic bradycardia or recurrent cardiogenic syncope
 - History of congenital long QT syndrome
 - Other medical or psychiatric condition including recent (within the past year) or active suicidal ideation/behavior, laboratory abnormality or other conditions that may increase the risk of study participation or, in the investigator's judgment, make the participant inappropriate for the study
- 2. Any condition possibly affecting drug absorption (eg, gastrectomy, cholecystectomy).
- 3. Known immunodeficiency disorder, including positive serology for HIV, or a first degree relative with a hereditary immunodeficiency.

- 4. Infection with hepatitis B or hepatitis C viruses according to protocol specific testing algorithm history.
 - For hepatitis B, all participants will undergo testing for HbsAg and HbcAb.
 - If HbsAg is positive, the participant must be excluded from participation in the study.
 - If HbsAg and HbcAb are both negative, the participant is eligible for study inclusion.
 - If HbsAg is negative and HbcAb is positive, HbsAb should be evaluated:
 - If HbsAb is negative, the participant must be excluded from participation in the study;
 - If HbsAb is positive, the participant is eligible for study inclusion.
 - For hepatitis C, all participants will undergo testing for HCVAb. Only participants who are HCVAb negative are eligible.
- 5. Participants with any of the following acute or chronic infections or infection history:
 - Any infection requiring treatment within 2 weeks prior to dosing.
 - Any infection requiring hospitalization or parenteral antimicrobial therapy within 60 days of the first dose of study intervention.
 - Any infection judged to be an opportunistic infection or clinically significant by the investigator, within the past 6 months of the first dose of study intervention.
 - Known active or history of recurrent bacterial, viral, fungal, mycobacterial or other infections.
 - History of recurrent (more than one episode of) localized dermatomal herpes zoster, or history of disseminated (single episode) herpes simplex or disseminated herpes zoster.
 - History of febrile illness within 5 days prior to the first dose of study intervention.
- 6. History of any lymphoproliferative disorder such as EBV related lymphoproliferative disorder, history of lymphoma, history of leukemia, or signs or symptoms suggestive of current lymphatic or lymphoid disease. Known present or a history of malignancy other than a successfully treated or excised nonmetastatic basal cell or squamous cell cancer of the skin or cervical carcinoma in situ.

- 7. Evidence of untreated or inadequately treated active or latent Mycobacterium TB infection as evidenced by the following:
 - A positive QFT-G test performed within the 12 weeks prior to screening. If the laboratory reports the test as indeterminate, the test should be repeated. If the result of the repeat test is indeterminate, a PPD test may be substituted for the QFT-G test only with approval from the Pfizer Medical Monitor on a case-by-case basis.
 - History of either untreated or inadequately treated latent or active TB infection.
 - If a participant has previously received an adequate course of therapy for either latent (9 months of isoniazid in a locale where rates of primary multi-drug resistant TB infection are <5% or an acceptable alternative regimen) or active (acceptable multi-drug regimen) TB infection, neither a QFT-G test nor a PPD test need be obtained. Details of the previous course of therapy (eg, medication(s) used, dose, duration of therapy) should be documented in the source documentation.
 - A participant who is currently being treated for active or latent TB infection must be excluded from the study.
- 8. Participants with ANY of the following abnormalities in clinical laboratory tests at screening or Day -1, as assessed by the study-specific laboratory and confirmed by a single repeat test, if deemed necessary:
 - WBC $<3500/\text{mm}^3$ ($<3.5 \times 10^9 \text{ cells/L}$)
 - ANC $<1500/\text{mm}^3$ ($<1.5 \times 10^9 \text{ cells/L}$)
 - ALC $< 800 / \text{mm}^3$ ($< 0.8 \times 10^9 \text{ cells/L}$)
 - Platelet count $<100/\text{mm}^3$ ($<100 \times 10^9$ cells/L)
 - Hemoglobin <10 g/dL
 - AST or ALT level > ULN;
 - Total bilirubin level > ULN; participants with a history of Gilbert's syndrome may have direct bilirubin measured and would be eligible for this study provided the direct bilirubin level is ≤ ULN;
 - Renal impairment as defined by an eGFR (units of mL/min/1.73m²) of <60 mL/min(/1.73m²). Based upon participant age at screening, eGFR will be calculated using the recommended CKD-EPI equation in Section 10.6.2 to determine eligibility (Screat-based formula)
 - In the opinion of the investigator or Pfizer (or designee), have any clinically significant laboratory abnormality that could affect interpretation of study data or the participant's participation in the study.

Prior/Concomitant Therapy:

9. Use of prescription or nonprescription drugs and dietary and herbal supplements within 5 half-lives plus 14 days prior to the first dose of study intervention. (Refer to Section 6.9 Prior and Concomitant Therapy for additional details).

Prior/Concurrent Clinical Study Experience:

10. Previous administration with an investigational product (drug or live or attenuated vaccine) within 30 days (or as determined by the local requirement) or 5 half-lives preceding the first dose of study intervention used in this study (whichever is longer).

Diagnostic Assessments:

- 11. A positive urine drug test.
- 12. A positive pregnancy test.
- 13. Screening or Day 1 prerandomization vital signs (taken in the supine position) with a HR <50 bpm OR systolic BP <90 mm Hg or ≥140 mm Hg OR diastolic BP <50 mm Hg or ≥90 mm Hg. Abnormal vital signs should be confirmed by 2 repeat measurements. Abnormal results that are confirmed on a repeat assessment are considered exclusionary.
- 14. Standard 12-lead ECG that demonstrates clinically relevant abnormalities that may affect participant safety or interpretation of study results (eg, QTcF >450 ms, complete LBBB, signs of an acute or indeterminate- age myocardial infarction, ST-T interval changes suggestive of myocardial ischemia, second- or third- degree AV block, or serious bradyarrhythmias or tachyarrhythmias). If QTcF exceeds 450 ms, or QRS exceeds 120 ms, the ECG should be repeated twice and the average of the 3 QTcF or QRS values used to determine the participant's eligibility. Computer-interpreted ECGs should be overread by a physician experienced in reading ECGs before excluding a participant.

Other Exclusion Criteria:

- 15. History of alcohol abuse or binge drinking and/or any other illicit drug use or dependence within 6 months of Screening. Binge drinking is defined as a pattern of 5 (male) and 4 (female) or more alcoholic drinks in about 2 hours. As a general rule, alcohol intake should not exceed 14 units per week (1 unit = 8 ounces (240 mL) beer, 1 ounce (30 mL) of 40% spirit, or 3 ounces (90 mL) of wine).
- 16. Use of tobacco/nicotine containing products in excess of 5 cigarettes/day.
- 17. WOCBP who are unwilling or unable to use an acceptable method of contraception as outlined in Section 10.4 during the intervention period and for at least 28 days after the last dose of study intervention.

- 18. History of severe allergic or anaphylactic reactions.
- 19. Unwilling or unable to comply with the criteria in the Lifestyle Considerations section of this protocol.
- 20. Investigator site staff directly involved in the conduct of the study and their family members, site staff otherwise supervised by the investigator, and sponsor and sponsor delegate employees directly involved in the conduct of the study and their family members.

5.3. Lifestyle Considerations

The following guidelines are provided:

5.3.1. Contraception

The investigator or their designee, in consultation with the participant, will confirm that the participant is utilizing an appropriate method of contraception for the individual participant and their partner(s) from the permitted list of contraception methods (see Appendix 4, Section 10.4.4) and will confirm that the participant has been instructed in its consistent and correct use. The investigator or designee will advise the participant to seek advice about the donation and cryopreservation of germ cells prior to the start of study intervention, if applicable.

At time points indicated in SoA, the investigator or designee will inform the participant of the need to use highly effective contraception consistently and correctly and document the conversation and the participant's affirmation in the participant's chart. Participants need to affirm their consistent and correct use of at least 1 of the selected methods of contraception, considering that their risk for pregnancy may have changed since the last visit.

In addition, the investigator or designee will instruct the participant to call immediately if the selected contraception method is discontinued and document the requirement to use an alternate protocol-specified method, including if the participant will no longer use abstinence as the selected contraception method, or if pregnancy is known or suspected in the participant or partner.

5.3.2. Meals and Dietary Restrictions

- Participants must abstain from all food and drink (except water) at least 4 hours prior to any safety laboratory evaluations and 10 hours prior to the collection of the predose PK sample.
- Water is permitted until 1 hour prior to study intervention administration. Water may be consumed without restriction beginning 1 hour after dosing. Noncaffeinated drinks (except grapefruit or grapefruit-related citrus fruit juices—see below) may be consumed with meals and the evening snack.
- Lunch will be provided approximately 4 hours after dosing.

- Dinner will be provided approximately 9 to 10 hours after dosing.
- An evening snack may be permitted.
- Participants will refrain from consuming red wine, grapefruit, or grapefruit-related citrus fruits (eg, Seville oranges, pomelos, fruit juices) from 7 days prior to the first dose of study intervention until collection of the final PK blood sample.
- While participants are confined, their total daily nutritional composition should be approximately 55% carbohydrate, 30% fat, and 15% protein. The daily caloric intake per participant should not exceed approximately 3200 kcal.

5.3.3. Caffeine, Alcohol, and Tobacco

Participants will abstain from caffeine-containing products for 24 hours prior to the start of dosing until collection of the final PK sample of each study period.

- Participants will abstain from alcohol for 24 hours prior (or as specified above for red
 wine) to admission to the CRU and continue abstaining from alcohol until collection
 of the final PK sample of each study period. Participants may undergo an alcohol
 breath test or blood alcohol test at the discretion of the investigator.
- Participants will abstain from the use of tobacco- or nicotine-containing products for 24 hours prior to dosing and during confinement in the CRU.

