Period 1 Study Days	-28 to -2	-1	1	2	3-8			Participants will be discharged from CRU on Day 2 of Period 1
Period 2 Study Days		9	10	11	12-17			 Minimum 8-day washout period between dosing in Periods 1 and 2 Participants will be discharged from CRU on Day 2 of Period 2.
CRU discharge				X				The participants will be discharged on Day 2 of each Period.
Participant Training for Micro PK Sampling, and Wearable Monitoring Devices, and recording of PK sampling times, concomitant medications and AEs				X#				# On Day 2 of Period 1, prior to discharge, participants will be trained on 1) use of devices (PCA500, BioBeat and Tasso) and provided with instruction materials for self-assessment of ECGs, vitals and PK samples, and 2) completion of diaries to record PK sampling times, concomitant medications and AEs In both Periods, participants will be provided with adequate supply of devices and diaries for remote self-assessment following discharge on Day 2
Serious and nonserious AE monitoring	X	\rightarrow	\rightarrow	→	\rightarrow	X	X	 See Section 8.4.3 for follow up AE and SAE assessments. AEs during Days 3-8 of both study Periods will be recorded on CRF by participants and if needed, reported to CRU by telephone.

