5.3.4. Activity

- Participants will abstain from strenuous exercise (eg, heavy lifting, weight training, calisthenics, aerobics) for at least 48 hours prior to each blood collection for clinical laboratory tests. Walking at a normal pace will be permitted;
- In order to standardize the conditions on PK sampling days, participants will be required to refrain from lying down (except ECG measurements), eating, and drinking beverages other than water during the first 4 hours after dosing.

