#### 6.2.2.1. First Dose HR reduction

Changes from predose baseline in HR at every hour up to 6 hours, at 8 and 24 hours on Day 1 and on Days 3 to 5, as well as the nadir HR value on Day 1 of each period, will be summarized by treatment.

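### The tobacco restriction stops at CRU discharge on Day 2, so for any tobacco user enrolled the home HR and BP changes on Days 3-5 may mix nicotine and drug effects, and no record of use is kept (minor; cheap to fix)

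*Protocol*

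**What the plan says.** **Restriction.** Protocol Section 5.3.3 asks participants to "abstain from the use of tobacco- or nicotine-containing products for 24 hours prior to dosing and during confinement in the CRU". The Schedule of Activities ends confinement early: "The participants will be discharged on Day 2 of each Period". The same section sets longer windows for two other substances. Participants must "abstain from caffeine-containing products for 24 hours prior to the start of dosing until collection of the final PK sample" of each period, and must "continue abstaining from alcohol until collection" of that same sample, which is due at 168 hours.

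**Eligibility.** Exclusion criterion 16 in Section 5.2 removes only heavier users: "Use of tobacco/nicotine containing products in excess of 5 cigarettes/day". Lighter users may enrol.

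**Home readings.** Under the Schedule of Activities, participants take their own ECG, pulse rate and BP on Days 3, 4 and 5 of both periods, at about the hour of the Day 1 dose. The diary covers PK sampling times, concomitant medications and adverse events. Tobacco is not among its items.

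**Analysis.** SAP 3.2.2.1 and 3.2.2.4 set the HR, BP and pulse rate baselines at predose on Day 1 of each period. SAP 6.2.2.1 summarises HR change from that baseline at the hourly times, "at 8 and 24 hours on Day 1 and on Days 3 to 5".

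**The concern.** A change score is easiest to read when baseline and follow-up are taken under like conditions. Here a tobacco user's baseline follows at least 24 hours without nicotine, while the Day 3-5 readings may follow a cigarette. A rule tied to confinement covers every reading in a fully confined study. In this hybrid design it lapses just as the remote readings begin.

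The effects that nicotine could disturb are ones the protocol sets out to watch. Section 4.2.1 describes heart-rate slowing, and Section 4.2.2 notes that "hypertension has been observed with S1P receptor modulators and AEs of hypertension have been reported". If nicotine raises HR and BP (an assumption, since neither document discusses it), it would offset any residual HR reduction and resemble a BP rise.

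The Day 3-5 readings also matter to the study's stated purpose. Remote collection of safety data is part of the rationale in Section 2.1, and safety assessed with wearable devices is a secondary objective. These three days are the only scheduled remote ECG, pulse rate and BP readings.

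**Working it through.** The plan gives no figure on this point to reproduce. The check compares the tobacco window with the measurement times, then illustrates size under stated assumptions.

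**Step 1: which readings fall inside the tobacco-free window** (Schedule of Activities; Section 5.3.3)

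| Reading, each period | Where taken | Tobacco barred? |
|---|---|---|
| Predose Day 1 (baseline) | CRU | Yes |
| 1, 2, 3, 4, 5, 6, 8 h | CRU | Yes |
| 24 h (Day 2, before discharge) | CRU | Yes |
| Days 3, 4, 5 | Home | No |

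Postdose times: 7 + 1 + 3 = 11. Covered: 8 of 11. Not covered: 3 of 11, and these are 3 of the 3 scheduled remote times.

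**Step 2: other text that might close the gap**

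- Section 8.3.2.2 bars smoking for 15 minutes before oral temperature. It does not apply to ECG, pulse rate or BP, and temperature is taken only predose on Day 1 within the periods.
- Section 8.3.3 requires at least 5 minutes of supine or near-supine rest before a scheduled ECG, and the Schedule of Activities puts vital signs after the ECG. This limits the effect of recent exertion. It does not address nicotine.
- Tobacco history is taken at screening and reviewed on Day -1, so users are known to the site. Use before a particular home reading is not recorded.

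Nothing extends the tobacco rule to Days 3-5.

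**Step 3: size, by illustration**

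Inputs: n = 8 (Section 9.5). The number of users k and the shift per user d are assumptions, because the documents give neither. The calculation also assumes that all 8 participants contribute and that each user has smoked shortly before the reading.

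Shift in mean change at a Day 3-5 time = k × d / 8

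| k users of 8 | d = 2 bpm | d = 5 bpm | d = 10 bpm | d = 15 bpm |
|---|---|---|---|---|
| 0 | 0 | 0 | 0 | 0 |
| 1 | 0.25 | 0.625 | 1.25 | 1.875 |
| 2 | 0.50 | 1.25 | 2.50 | 3.75 |
| 3 | 0.75 | 1.875 | 3.75 | 5.625 |

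Example: two users at 10 bpm give 2 × 10 / 8 = 2.5 bpm. The same formula applies to BP in mm Hg for whatever shift is assumed. An individual user's own change moves by the full d, which shows in a listing of 8 people.

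**The case against.** The strongest reply is that little depends on these readings. That largely stands, and it limits what may be inferred.

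- A reader might infer that smoking could hide the first-dose HR reduction. The documents do not support this. Section 2.3.1 describes the reduction as greatest on the first dosing day, and every Day 1 reading, the nadir and the 24-hour reading are taken under the tobacco ban. Only a residual effect on Days 3-5 could be obscured, and Section 2.2.4.2 describes the HR effects as transient.
- A reader might infer a bias between Treatments G and F. The same rule applies in both periods, so none is expected if habits are stable. No hypothesis is tested, the safety summaries are descriptive, and the primary endpoints are pharmacokinetic.
- A reader might infer distortion of the QTcF summaries. The documents give no direction or size for such an effect, and QTcF is already corrected for rate.
- A reader might infer that nothing allows the effects to be told apart. That goes too far. Users are identifiable from their history, and the SAP lists vital signs and ECG data, so their values can be inspected. What is missing is a record of use before each reading.
- The caffeine and alcohol windows are tied to the last PK sample, so the shorter tobacco window is not a contradiction. The comparison shows only that a restriction continuing at home is already accepted in this study.
- Exercise is similarly uncontrolled on Days 3-5, since Section 5.3.4 restricts it only "for at least 48 hours prior to each blood collection for clinical laboratory tests". The rest required before ECGs partly answers this, so it adds little weight.

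What survives is that for tobacco users the remote readings are taken under different conditions from their baseline, and nothing records when.

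**Conclusion.** The gap is real and minor. For any tobacco user enrolled, HR and BP change on Days 3-5 may combine nicotine and drug effects, and the affected readings cannot be picked out individually. There is no effect if no users enrol. With one to three users of 8 and an assumed shift of 5 to 15 bpm, the mean Day 3-5 change would move by 0.625 to 5.625 bpm; with one user at 2 bpm it would move by 0.25 bpm. The number of users, the size and direction of the shift, and smoking shortly before each reading are all assumptions. The point is worth acting on because the three times concerned are the whole of the scheduled remote ECG, pulse rate and BP data, and the remedy costs little.

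**What to change.** 1. In Protocol Section 5.3.3, require no tobacco or nicotine on the morning of each Day 3, 4 and 5 reading until that reading is complete. Alternatively, run the existing restriction through the Day 5 readings of each period.
2. Add a diary item asking whether tobacco or nicotine was used before each Day 3-5 reading, and when.
3. In the SAP, flag affected values in the Day 3-5 HR, pulse rate and BP listings, and footnote the summaries.

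If the sponsor prefers to leave home behaviour unrestricted, items 2 and 3 alone would make the readings interpretable.

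The cost is a line of protocol text, one diary item and a listing flag. The downside is a short extra restriction at home for light users, and reliance on self-report.
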